### **3.8.1 Safety consideration**

To ensure safety throughout the study, comprehensive measures were implemented across all stages: Prior to the experiment, participants were subjected to thorough health screenings, including medical history reviews and baseline physical assessments (e.g., BMI, musculoskeletal evaluations), to confirm eligibility and identify potential risks. Training sessions emphasized the importance of proper warm-up routines, standardized movement execution, and immediate reporting of discomfort, with all participants signing written documents to acknowledge risks, benefits, and withdrawal rights. During the intervention, training took place in a FIG-certified facility equipped with Olympic-grade apparatus and shock-absorbing flooring, supervised by three certified instructors. Real-time heart rate monitoring via Xiaomi Smart Bands ensured intensity levels remained within the prescribed range (80–140 bpm). For high-risk maneuvers such as balance beam dismounts, spotters and crash mats were deployed. In case of falls or acute pain, activities were immediately halted, and emergency protocols—including on-site first-aid personnel and equipment—were activated. Post-experiment, participants completed cooldown routines and underwent follow-up assessments to monitor for delayed soreness or adverse effects. All health and performance data were anonymized in accordance with institutional privacy policies to protect confidentiality. A continuous communication channel was maintained after the study to address any ongoing concerns.

### **3.8.2 Research tool**

#### **3.8.2.1 Kunwei Force Plate (jumping test)**

The Kunwei force plate is a high-precision biomechanical measurement device widely used to assess jump performance, balance, and force development in athletes (Cormie et al., 2007). To scientifically evaluate the biomechanical performance of the countermovement jump (CMJ) and single-leg countermovement jump (SLCMJ), the standardized testing protocol using the

Kunwei Force Plate is as follows: Participants stand barefoot on the force plate with arms relaxed to complete a 10-second static calibration, recording baseline center of pressure (CoP) trajectories (re-test required if CoP drift exceeds 2 cm), with the system sampling rate set to 1000 Hz. For CMJ testing, participants perform rapid countermovement jumps from self-selected knee flexion depth to maximal height, landing symmetrically and stabilizing for 2 seconds, repeated 5 times (60-second rest intervals) (Markovic et al., 2004). For SLCMJ, participants execute single-leg jumps followed by ipsilateral landing with 3-second balance maintenance; failed trials (contralateral limb contact or external support) trigger retesting. The force plate continuously acquires vertical ground reaction force (vGRF) to calculate jump height (flight time method:  $h = \frac{g \times t^2}{8}$  ) peak force (max vGRF), rate of force development (RFD: slope of force-time curve from 0-200 ms), and impulse (force-time integral). Real-time feedback on adjacent screens highlights critical metrics (e.g., RFD < 3000 N/s—optimize ankle stiffness or bilateral peak force asymmetry > 10%—adjust symmetry). Raw data undergo Butterworth low-pass filtering (50 Hz cutoff) and body weight normalization, with outliers excluded based on predefined criteria (e.g., pre-activation force exceeding 5% body weight or stabilization time > 1.5 seconds). Processed datasets are encrypted and stored as CMJ/SLCMJ-Date-Subject. This protocol quantifies lower-limb explosive power, bilateral symmetry, and energy transfer efficiency (Gathercole et al., 2015), supporting athlete selection, training monitoring, and rehabilitation assessment (Meylan & Malatesta, 2009).

Figure 11 Kunwei Force Plate

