## **1.6 Definitions of Operational Terms**

There operational terms used in this research proposal are shown below:

Static Balance:	The ability to regulate the body's center of gravity in a relatively stationary state (Halabchi et al., 2020).
Dynamic Balance:	The ability to regulate the body's center of gravity and adjust posture during movement (Lu et al., 2022).
Stability:	The inherent characteristic of an object to maintain or restore balance and avoid tipping over (Abadi Marand et al., 2023).
Human Stability:	The inherent ability of the human body, through the motor system, sensory system, and individual characteristics, to maintain, achieve, or restore balance and prevent falling (Thomas et al., 2019).
Jump or Leap in Gymnastics:	A skill in which athletes use lower body strength to propel themselves off the ground, perform specific movements or postures in the air, and land steadily (Suchomel et al., 2016).
Beginner Gymnasts:	Gymnasts with less than 1 year of systematic training experience in gymnastics, have not yet acquired complex gymnastic skills, and are in a phase of rapid development regarding fundamental physical fitness and motor skills. (Vickers, 1988).

Kinesiology in Gymnastics:	Kinesiology in gymnastics mainly describes the characteristics of athletes' movements (Al-Jaafreh & Qawaqzeh, 2024).
Definition of Biomechanics in Gymnastics:	Biomechanics in gymnastics combines biological and mechanical principles to study the laws of athletes' mechanical movements (Bartlett, 2014).
Peak Force:	During the concentric contraction phase (i.e., from the lowest point of the squat during the push-off until just before toe-off), the ground reaction force (GRF) gradually increases as the muscles generate force, and the highest force value within this phase is defined as the peak force (Kim et al., 2022).
Rate of Force Development:	The rate of force development (RFD) in countermovement jumps refers to the rate at which ground reaction force (GRF) changes over time during the concentric contraction phase (from the lowest squat point to just before takeoff) (Mackala et al., 2013), reflecting the neuromuscular system's ability to generate force rapidly and directly determining explosive takeoff power (Djurić et al., 2023).

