Impulse:	In countermovement jumps, impulse is the accumulation of ground reaction force (GRF) over time (the area under the force-time curve) (Claudino et al., 2017). Its net impulse (total impulse minus gravitational impulse) determines the change in human momentum, directly dictating the takeoff velocity and jump height (Painter et al., 2022).
Center of gravity deviation distance	In rotational movements, the center of gravity deviation distance refers to the perpendicular deviation distance of the center of gravity (CoG) relative to the rotation axis—the smaller the deviation, the higher the efficiency of rotational control (Lee et al., 2021).
Joint Angle variation	It refers to the dynamic angular changes in each joint relative to the initial posture, which regulates the moment of inertia and angular momentum by adjusting joint flexion/extension to achieve precise control over rotational speed and stability (Moke et al., 2020).

Vertical Jump Efficiency	It refers to the ability to convert energy generated by muscle contraction (especially the elastic energy stored during the eccentric-concentric contraction cycle and the energy from active force generation) into the gravitational potential energy required for the vertical displacement of the body's center of mass (Kazuaki et al., 2022).
Landing Impact Force	It refers to the instantaneous peak force generated by the ground reaction force (GRF) now the body contacts the ground (Mojaddarasil & Sadigh, 2021a).
Body Oscillation Amplitude	It refers to the maximum displacement of the body's center of mass (or specific segments) relative to the equilibrium position during dynamic movements such as running, jumping, and walking (Pettorossi et al., 2013).
Rotation Smoothness Index	It is a quantitative index used to evaluate the smoothness of the angular velocity time series in rotational movements (such as gymnastic twists and figure skating spins) (Sjölander et al., 2008).

## CHAPTER 2

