### 3.2.2.2 Countermovement Jump

The participant begins in a standing position with feet shoulder-width apart and arms relaxed. Upon initiation, the athlete rapidly performs a countermovement by flexing the hips and knees to approximately 90° between the trunk and thighs, followed by explosive vertical propulsion through coordinated hip and knee extension, synchronized with upward arm swing to ear level (Hou et al., 2025). During the airborne phase, the body remains upright, and upon landing, the athlete transitions from forefoot to full-foot contact while maintaining stability, with post-landing knee flexion limited to  $\leq 30^\circ$  to minimize impact forces (Morin et al., 2011) (see Figure 5 for movement breakdown).

[figure not shown]
Force plates are utilized to record ground reaction forces (GRF) across all phases (countermovement, takeoff, and landing) (Myer et al., 2008). Jump height is calculated via the impulse-momentum method by integrating force-time data from the countermovement phase to takeoff (Weyand et al., 2000). Key parameters—including rate of force development (RFD), peak force magnitude, force-time curve symmetry, and force attenuation gradients during the initial 200 ms of landing—are analyzed to quantify lower limb stiffness, neuromuscular coordination, and dynamic stability. Notably, landing-phase force decay patterns correlate with knee joint stability and serve as predictive indicators of injury risk (Higashihara et al., 2018; Myer et al., 2011).

Figure 5 Countermovement Jump

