### 3.2.2.3 Single - Leg Countermovement Jump

Participants stand on one leg on a force platform, with the non-supporting leg flexed at approximately  $90^\circ$  at the knee and hands on hips to maintain an upright posture (Sharrock et al., 2011). At the start of the test, subjects perform a rapid countermovement by coordinated flexion of the hip and knee (with a trunk-thigh angle of approximately  $45^\circ$ ), followed by an explosive single-leg extension to jump vertically, synchronizing arm swing to enhance momentum. During the aerial phase, a neutral pelvic position must be maintained. Upon landing, subjects make contact with the forefoot and maintain knee flexion  $\leq 25^\circ$ , avoiding compensatory trunk tilt or swinging of the non-supporting leg throughout the movement (Hibbs et al., 2008), the decomposed movements are shown in Figure 6.

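### The HA2 jump outcomes have conflicting definitions and test instructions; as section 3.8.2.1 is written, peak force can pick up the landing, and jump height has two methods

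*Protocol*

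**What the plan says.** - **Peak force.** Section 1.6 confines it to the push-off, from the lowest squat point to just before toe-off: "the highest force value within this phase is defined as the peak force". Section 2.5.1 also ties it to take-off. Section 3.8.2.1, the testing procedure, has "peak force (max vGRF), rate of force development (RFD: slope of force-time curve from 0-200 ms" with no phase limit. It has the plate recording continuously while the participant lands and then stabilises (2 s in the countermovement jump, CMJ; 3 s in the single-leg version). Section 3.2.2.2 confirms the span: "Force plates are utilized to record ground reaction forces (GRF) across all phases (countermovement, takeoff, and landing".
- **Jump height.** Section 3.2.2.2 uses the impulse-momentum method; 3.8.2.1 uses flight time, g·t²/8.
- **Arms in the single-leg jump.** Section 3.2.2.3 asks for "hands on hips to maintain an upright posture" and, in the next sentence, "synchronizing arm swing to enhance momentum".
- **CMJ depth.** Section 3.2.2.2 prescribes "flexing the hips and knees to approximately 90° between the trunk and thighs"; 3.8.2.1 has jumps "from self-selected knee flexion depth to maximal height".
- **Scale.** Section 3.8.2.1 normalises the data to body weight; Table 17 reports peak force in N and impulse in N·s.
- **Rate of force development (RFD) and impulse.** Section 1.6 places RFD in the concentric phase; 3.8.2.1 uses a 0-200 ms slope without saying what event is time zero. Section 1.6 describes impulse as the area under the force-time curve and adds: "Its net impulse (total impulse minus gravitational impulse) determines the change in human momentum". Section 3.8.2.1 calls it the force-time integral, with no window and no statement of gross or net. Table 17 as read gives RFD in N·s, while 2.5.1 and 3.8.2.1 use N·s⁻¹ and N/s.

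**The concern.** Specific objective 2 and HA2 rest on these measures. The two peak-force rules look at different phases of the jump, and the desirable direction differs between them: the protocol treats lower landing force as better (research question 3, section 3.2.3.2.4), while peak force under HA2 is meant to show jumping capacity. If the landing peak is recorded as peak force, a participant who learns to land more softly appears to jump with less force.

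This need not be equal across arms. Landing control training is scheduled in the dynamic arm (Table 14, week 7) and the combined arm (Table 15, weeks 4 and 7), but not in the static arm (Table 13). The error could therefore become a difference between arms.

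The arm and depth conflicts work differently. They let the test itself vary between testers or between the two visits, which adds error to change scores in groups of 15.

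**Working it through.** The protocol states no figure to reproduce. It gives no jump height, body mass or force data, so every mechanical value below is an assumption used to show size.

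**1. Can landing force exceed push-off force?** By energy balance, mean vertical force in body weights (BW) is 1 + h/d, where h is jump height and d the travel of the centre of mass in that phase. Assume h = 0.25 m.
- Push-off, d = 0.30 m: 1 + 0.25/0.30 = 1.83 BW.
- Landing, d = 0.10 m: 3.50 BW; d = 0.20 m: 2.25 BW; d = 0.30 m: 1.83 BW, equal to push-off.

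Landing force is larger whenever landing travel is shorter than push-off travel. Section 3.2.2.2 limits knee flexion after landing to 30°, which favours a short landing.

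**2. What does each peak-force rule return?** Take-off velocity is v = √(2 × 9.81 × 0.25) = 2.215 m/s, so v/g = 0.2258 s. For a half-sine landing absorbed over T seconds, the landing peak is 1 + (π/2)(0.2258/T). The push-off peak in the same assumed trace is 1.95 BW.

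| T (s) | Landing peak (BW) | Concentric rule, 1.6 | Whole-record maximum, 3.8.2.1 |
|---|---|---|---|
| 0.10 | 4.55 | 1.95 | 4.55 |
| 0.15 | 3.36 | 1.95 | 3.36 |
| 0.20 | 2.77 | 1.95 | 2.77 |
| 0.30 | 2.18 | 1.95 | 2.18 |
| 0.40 | 1.89 | 1.95 | 1.95 |

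If absorption time lengthened from 0.15 to 0.20 s with an identical push-off, the literal rule would report a fall from 3.36 to 2.77 BW.

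**3. Do the two jump-height methods agree?** Only if the body is at the same height at landing and take-off. If it lands lower by δ, flight time is v/g + √(2(h + δ)/g).
- δ = 0.02 m: t = 0.2258 + 0.2346 = 0.4604 s, and g·t²/8 = 0.260 m (+4.0%).
- δ = 0.05 m: t = 0.2258 + 0.2473 = 0.4731 s, and g·t²/8 = 0.274 m (+9.8%).

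Impulse-momentum height does not carry this error. A constant error cancels in a within-person change; one that shifts with landing posture does not.

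**4. How much is left open for RFD and impulse?** In the assumed trace the 0-200 ms slope is -2.68 BW/s from movement onset, +4.62 from the start of braking and -1.04 from the lowest point, so even its sign depends on time zero. For 55 kg, net impulse is 55 × 2.215 = 121.8 N·s. Adding gravity (55 × 9.81 × 0.6 = 323.7; × 1.0 = 539.6) gives a gross impulse of 445.5 to 661.4 N·s over 0.6 to 1.0 s. These show the size of an open choice, not of a contradiction.

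**5. How many outcomes are affected?** Height has two methods; peak force has two windows and two scales; RFD has no start event; impulse has no window, no gross-or-net rule and two scales. That is 4 measures × 2 jump tests = 8 of 8.

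**The case against.** The best defence is that section 1.6 is the operational definition, section 2.5.1 agrees with it, and landing impact force is a separately named quantity. On that view the 3.8.2.1 wording is shorthand. This shows what is intended, and it rules out claiming that the trial will report landing force or that HA2 will come out reversed. It also takes a stiff enough landing: at 0.40 s nothing changes. But 3.8.2.1 is the procedure an operator or processing routine would follow, and it does not carry the window over.

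Three stronger readings are tempting and should not be made.
- A reader might infer that impulse is net in 1.6 and gross in 3.8.2.1. Section 1.6 first defines impulse as the whole area under the curve and only then says what its net part determines. The choice is unstated, not contradictory.
- A reader might infer that the two RFD definitions are incompatible. A 200 ms window can start within the concentric phase; only the start event is missing.
- A reader might call N·s for RFD in Table 17 an error. A superscript lost in reading the table would produce the same text.

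On depth, one section speaks of the trunk-thigh angle and the other of knee flexion, so the clash is looser than it first looks. A prescribed posture and a self-selected depth still cannot both serve as the instruction. No such defence is available for the arm instruction, for jump height, or for normalised data against N and N·s.

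**Conclusion.** The point holds. Five conflicts stand on the text alone: the peak-force window, the jump-height method, the single-leg arm position, the CMJ depth and the scale. The RFD start event, the impulse definition and the Table 17 RFD unit are lesser matters of completion.

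That the 3.8.2.1 rule can return the landing peak rests on landing travel being shorter than push-off travel. Under the assumed values, the recorded peak would be about 1.1 to 2.3 times the intended one (2.18/1.95 to 4.55/1.95) for absorption times of 0.30 to 0.10 s, and unchanged at 0.40 s. Whether training would change landing stiffness enough to shift a comparison between arms is not known from the protocol.

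**What to change.** In 3.8.2.1, restrict peak force to the concentric phase as in 1.6, and name the RFD start event within that phase. Check on pilot traces that a 200 ms window suits it, given the negative slope from the lowest point in the illustration. Use one jump-height method in 3.2.2.2 and 3.8.2.1. State impulse as net impulse up to take-off, because 1.6 says that this part dictates take-off velocity and jump height. Use one scale in 3.8.2.1 and Table 17, and have the RFD unit there read N·s⁻¹ if it does not already.

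Before baseline testing, set one arm instruction for the single-leg jump and one depth instruction for the CMJ, identical at both visits.

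The cost is wording and units. The outcome definitions can be computed from the same recordings, even later. The arm and depth instructions change what is recorded and cannot be put right afterwards. Table 22 dates data collection to 1/9/2026.

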## 4.2 Jumping ability test results

Table 17 Countermovement jump (CMJ) and single-leg countermovement jump tests at baseline and after 8 weeks in the static intervention, dynamic intervention, static-dynamic intervention, and control groups. Data presented as mean  $\pm$  SD.

Group	Test Type	Time Point	Jump Height (Mean $\pm$ SD)	Peak Force (N) (Mean $\pm$ SD)	Rate of Force Development (N·s) (Mean $\pm$ SD)	Impulse (N·s) (Mean $\pm$ SD)	Two-Way Repeated Measures ANOVA	Bonferroni (p)
Static balance group	Countermovement jump	B						
		W8						
	Single-leg countermovement jump	B						
		W8						
Dynamic balance group	Countermovement jump	B						
		W8						
	Single-leg countermovement jump	B						
		W8						
Static and Dynamic balance group	Countermovement jump	B						
		W8						
	Single-leg countermovement jump	B						
		W8						
Control group	Countermovement jump	B						
		W8						
	Single-leg countermovement jump	B						
		W8						

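### Impulse is scored as a gross force-time integral with no body-weight subtraction or fixed window, so it mixes jump performance with movement duration and can move opposite to the net impulse that section 1.6 says determines jump height

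*Protocol*

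**What the plan says.** Section 3.8.2.1 is the operative scoring rule. It says "The force plate continuously acquires vertical ground reaction force (vGRF" and then lists what is calculated from that signal: jump height, peak force, rate of force development, "and impulse (force-time integral". No body-weight term is subtracted and no integration limits are given for impulse. The same section says "Raw data undergo Butterworth low-pass filtering (50 Hz cutoff) and body weight normalization", without saying what is divided by what. It describes the CMJ as "rapid countermovement jumps from self-selected knee flexion depth to maximal height".

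Section 1.6 opens its definition the same way: in countermovement jumps "impulse is the accumulation of ground reaction force (GRF) over time (the area under the force-time curve". It then adds: "Its net impulse (total impulse minus gravitational impulse) determines the change in human momentum, directly dictating the takeoff velocity and jump height".

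Table 17 (section 4.2) has one impulse column, headed "Impulse (N·s) (Mean $\pm$ SD", for CMJ and SLCMJ at baseline and week 8 in all four arms, with a two-way repeated measures ANOVA and Bonferroni comparisons. Net impulse is not listed as an outcome anywhere. Research question 2 (section 1.3) counts impulse among four jumping-mechanics measures in which improvement is looked for, and specific objective 2 lists it among the measures whose change is studied.

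The only integration window in the protocol is in section 3.2.2.2, "integrating force-time data from the countermovement phase to takeoff", and it is given for jump height, not for impulse.

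**The concern.** The protocol scores one quantity while its own definition says that a different one carries the mechanical meaning. The gross integral contains body weight multiplied by the time over which force is integrated. That part says nothing about how high or how powerfully the participant jumps, yet it changes whenever movement time changes. Depth is self-selected in section 3.8.2.1. The approximate trunk-thigh angles in sections 3.2.2.2 and 3.2.2.3 would guide depth but do not fix movement time.

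If training changes movement time differently between arms, the group-by-time comparison on impulse can show a difference without any difference in jumping, hide a real one, or point the wrong way. A reader of Table 17 who takes a higher impulse as a better jump, as research question 2 invites, could then draw the wrong conclusion about which training mode works.

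**Working it through.** The protocol states no impulse value, movement duration or expected jump height, so there is no figure of its own to reproduce. Body mass (55 kg), durations and heights below are assumptions; g = 9.81 m/s².

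**Identity.** If the window starts at zero vertical velocity (quiet standing, or the lowest point of the squat) and ends at take-off:

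- take-off velocity: v = √(2gh)
- net impulse = m·v
- gross impulse = m·v + m·g·T, where T is the window length
- body-weight share of gross = gT / (gT + v), which does not depend on mass

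**Body-weight share.**

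- Countermovement onset to take-off, T 0.6-0.9 s, h 0.20-0.30 m. Lowest: 5.886 / (5.886 + 2.426) = 71%. Highest: 8.829 / (8.829 + 1.981) = 82%.
- Same window at assumed single-leg heights of 0.10-0.15 m, T 0.6-0.8 s: 77-85%.
- Concentric phase only, T 0.20-0.30 s, h 0.20-0.30 m. Lowest: 1.962 / (1.962 + 2.426) = 45%. Highest: 2.943 / (2.943 + 1.981) = 60%.

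**Direction of change, onset to take-off, 55 kg.**

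| Jump | Net (N·s) | Body weight × T (N·s) | Gross (N·s) | Gross vs reference |
|---|---|---|---|---|
| Reference: 0.25 m, 0.75 s | 121.8 | 404.7 | 526.5 | |
| Higher and faster: 0.27 m, 0.65 s | 126.6 (+4%) | 350.7 | 477.3 | -9% |
| Same height, slower: 0.25 m, 0.85 s | 121.8 (0%) | 458.6 | 580.4 | +10% |
| Higher, same time: 0.27 m, 0.75 s | 126.6 (+4%) | 404.7 | 531.3 | +0.9% |

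The last row shows that when movement time is unchanged the direction is right, but a 4% gain in net impulse shrinks to under 1% of the gross score.

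**Concentric window.** 0.25 m in 0.30 s gives 121.8 + 161.9 = 283.7 N·s. 0.28 m in 0.27 s gives 128.9 + 145.7 = 274.6 N·s. Net rises 5.8% while gross falls 3.2%, so the reversal does not depend on choosing the longer window.

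**How little shortening is needed.** Gross impulse is unchanged when T shortens by (v₂ - v₁)/g. From 0.25 to 0.28 m this is (2.344 - 2.215)/9.81 ≈ 0.013 s, whatever the mass or total duration. Any greater shortening turns the gain into an apparent loss.

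**Does normalization help?** Dividing gross impulse by body weight gives T + v/g. For the first two rows of the table: 0.75 + 0.226 = 0.976 s and 0.65 + 0.235 = 0.885 s, still 9% lower. Dividing by mass gives gT + v, with the same ordering. Neither is in N·s, the unit in Table 17.

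**The case against.** The strongest reply is that the phrase in section 3.8.2.1 is a short gloss. Net impulse is also a force-time integral, and section 1.6 shows that the authors know which impulse matters. On that view this is an ambiguity that the analysis plan could settle. Part of this stands: an analyst might compute net impulse. But the scoring section applies the integral to the raw vertical force, the definition's first sentence equates impulse with the full area, and net impulse appears only as an explanation of mechanics. Followed as written, the text yields the gross value, so the rule is badly stated and not merely left for later.

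A second reply is that body-weight normalization deals with the problem. If it means division, it removes most of the dependence on participant mass, so a reader should not infer that heavier participants necessarily score higher. It leaves the duration term in place.

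Three stronger readings are tempting, and the documents do not support them.

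- A reader might infer that a fixed three quarters of the score is body weight. The protocol fixes neither window, duration nor height, so only a conditional range can be given.
- A reader might infer, from the continuous recording and the 2-second stabilisation, that landing is included. Net impulse from rest to rest is zero, so the score would then be purely body weight times time. But section 2.5.1 lists impulse among take-off indicators and section 1.6 ties it to take-off velocity, so nothing points to that window.
- A reader might infer that the training will shorten the movement and so reverse the result. The protocol gives no evidence on movement time. The reversal is possible, not predicted.

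Finally, hypothesis HA2 names the two jump tests, not impulse. The link to improvement runs through research question 2 and Table 17.

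**Conclusion.** The point holds in conditional form. As written, the impulse outcome is gross impulse, which the protocol's own definition distinguishes from the quantity that determines jump height. It can fall when a jump becomes faster and higher, and rise when the movement is only slower. This is true for either plausible take-off window and is not cured by dividing by body weight.

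The size rests on assumed values. A 0.1 s change in movement time moves the gross score by about 10%, against about 4% in net impulse for a 2 cm gain in height. The percentages do not depend on the assumed 55 kg. They do depend on the assumed durations and heights.

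The reach is limited to one of four jump measures, in both CMJ and SLCMJ. The scores for jump height, peak force and rate of force development do not use this integral as section 3.8.2.1 defines them. The correction is worth making before data are processed, but it does not threaten the trial as a whole.

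**What to change.** In section 3.8.2.1, define the impulse outcome as net vertical impulse: the integral of vertical ground reaction force minus body weight, from a stated movement-onset criterion to take-off. Take body weight from the mean vertical force during the planned 10-second static stand. That stand is described as recording centre-of-pressure trajectories, so add that its vertical force is kept. State what body-weight normalization means and to which variables it applies. Head the Table 17 column net impulse, in N·s, or N·s/kg if divided by mass. In section 1.6, say that the outcome is net impulse.

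The cost is a few lines of text. The force plate, the sampling rate and the static stand are already planned.

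The downside is redundancy. Net impulse per kilogram equals take-off velocity and so largely repeats jump height, adding little independent evidence. If the gross integral is kept for other reasons, report it descriptively only, next to movement time.
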